3.2 Data Review Committee

A DRC comprised of members with pertinent expertise will review emerging safety, efficacy, and PK data at appropriate times throughout the study, as described in this protocol and as set forth in the DRC Charter.

The DRC will convene throughout the study to review safety and PK data to recommend if it is safe and appropriate to continue the study as planned. The DRC will convene to recommend if continuation of Part 1, Step 1 and Part 1, Step 2 as planned is acceptable or if dosing modifications are required once AE information through at least 8 hours following the first dose of study drug is available for all 6 sentinel subjects in both Step 1 and Step 2 of Part 1. Upon both reviews after Part 1, Step 1 and Part 1, Step 2, the DRC will recommend subsequent dosing regimen(s) to be tested in the study. Prior to the initiation of Part 2, the DRC may also make a recommendation to increase the study drug dosing duration to up to 14 days. The highest dose in this study will not exceed 30 mg TID. The DRC can request to unblind efficacy data at any point if deemed necessary to adequately complete their review. Additionally, the DRC may request to unblind efficacy data

if an increase in the study drug dosing duration is under consideration. Further details regarding the role, responsibilities, and procedures of the DRC will be provided in the DRC Charter.

In addition, ad hoc reviews of safety data will be performed throughout the study by appropriate study personnel and the Medical Monitor.

3.3 Study Indication

The indication for this study is moderate to severe COVID-19.

4 SELECTION AND WITHDRAWAL OF SUBJECTS

4.1 Inclusion Criteria

Subjects who meet all of the following criteria will be eligible to participate in the study:

1. Ability to understand and provide informed consent;

Note: where permitted by local regulations, in cases where a prospective subject's diminished mental capacity affects his or her capability to provide informed consent, consent provided by a legally authorized representative (LAR) is allowed. If the subject regains decision-making mental capacity during conduct of the study, the subject will be reconsented at the earliest opportunity.

2. Males and non-pregnant females ≥ 18 years of age at the time of Screening;
3. Laboratory-confirmed active SARS-CoV-2 infection as determined by polymerase chain reaction (PCR) or other commercial or public health assay in any specimen, as documented by either of the following:
 - o SARS-CoV-2 PCR positive in sample collected <72 hours prior to randomization; OR
 - o SARS-CoV-2 PCR positive in sample collected ≥ 72 hours prior to randomization, documented inability to obtain a repeat sample (eg, due to lack of testing supplies, limited testing capacity, results taking >24 hours to obtain, etc), AND progressive disease suggestive of ongoing SARS-CoV-2 infection;
4. Females of childbearing potential must be willing to completely abstain or agree to use a highly effective method of contraception (ie, less than 1% failure rate) from the time of signing the ICF and for the duration of study participation (through Day 28); and
 - o Note: Females of childbearing potential must have a negative urine pregnancy test during Screening. A female of childbearing potential is any female, regardless of sexual orientation, who meets the following criteria: has not undergone a hysterectomy or bilateral oophorectomy or has not been naturally postmenopausal for at least 12 consecutive months (ie, has had menses at any time in the preceding 12 consecutive months).
5. Currently hospitalized, receiving standard of care therapy for COVID-19, and meets the criteria for moderate or severe COVID-19 as follows:

Moderate COVID-19 (Note: Subjects with moderate COVID-19 will comprise a maximum of approximately 50% of the subjects enrolled in each of the following: Part 1, Step 1; Part 1, Step 2; and Part 2.)

- o Symptoms of moderate illness with COVID-19, which could include shortness of breath with exertion, fever, dry cough, headache, body aches, chills, loss of taste or smell, etc; and
- o Respiratory rate ≥ 20 breaths per minute, $\text{SpO}_2 > 93\%$ on room air at sea level, or heart rate ≥ 90 beats per minute.

OR

Severe COVID-19

- Symptoms suggestive of severe systemic illness with COVID-19, which could include shortness of breath at rest or respiratory distress; and
- Respiratory rate ≥ 30 breaths per minute, heart rate ≥ 125 beats per minute, or $\text{SpO}_2 \leq 93\%$ on room air at sea level or $\text{PaO}_2:\text{FiO}_2 < 300$.

Note: Patients receiving high flow oxygen by a nasal cannula or noninvasive positive pressure ventilation are permitted.

4.2 Exclusion Criteria

Subjects who meet any of the following criteria will be excluded from participation in the study:

1. Inability to initiate study drug within 12 hours after randomization;
2. Female of childbearing potential who is unable or unwilling to forego breastfeeding through Day 28;
3. Systolic blood pressure < 100 mmHg;
4. In shock or requiring pressor support;
5. Subjects who are on invasive mechanical ventilation; are receiving oxygen delivered by extracorporeal membrane oxygenation (ECMO); or have clinical need for 1 of the preceding therapies, but preceding therapies not able to be administered in setting of resource limitation;
6. Alanine aminotransferase (ALT) or aspartate aminotransferase (AST) $> 3 \times$ the upper limit of normal (ULN);
7. Total bilirubin $> 2 \times$ ULN;
8. Estimated glomerular filtration rate < 30 mL/min or receiving hemodialysis or hemofiltration;
9. Moribund subject not expected to survive 24 hours in the opinion of the treating clinical team;
10. Any concurrent serious medical condition (eg, active malignancies on chemotherapy, post-organ transplant, end stage congestive heart failure) or not likely to respond to treatment;
11. Decision to withhold life-sustaining treatment;

Note: In the event of cardiac arrest, the decision to withhold cardiopulmonary resuscitation only does not fulfill this exclusion criterion.

12. Use of sensitive substrates of cytochrome P450 (CYP) 2C8 (eg, repaglinide, paclitaxel, or cerivastatin);
13. Use of CYP2C8 inhibitors (eg, gemfibrozil, fluvoxamine, or ketoconazole);
14. Participation in another investigational study during the present study through the last visit (Day 28); or
15. Previous randomization in this study.

4.3 Retesting

If laboratory abnormalities during Screening are considered by the Investigator to be transient, then the laboratory tests may be repeated once within the Screening window. The Investigator's

rationale for retesting should be documented. If the retest result is no longer exclusionary, the subject may be randomized.

4.4 Stopping Criteria

4.4.1 Criteria for Discontinuation of Study Drug in Individual Subjects

Subjects will be discontinued from study drug, but will continue to be followed in the study, if they experience any of the following:

- \geq Grade 3 (Common Terminology Criteria for Adverse Events [CTCAE] version 5.0) AE or clinically significant laboratory abnormality considered related to study drug;
- \geq Grade 3 (CTCAE version 5.0) injection reaction in the first 24 hours post-injection;
- Significant drop in the subject's blood pressure such that medical intervention is necessary (ie, \geq Grade 3 [CTCAE version 5.0] AE), a blood pressure $<80/60$ that is considered related to study drug, or lack of response to simple measures such as postural change (eg, supine with legs raised) or oral or intravenous bolus; and/or
- Anaphylactic reaction that is moderate or severe, or any anaphylactic reaction that requires emergency medical management.

For any subject who prematurely discontinues from study drug, the reason and date of discontinuation will be documented in the source and electronic case report forms (eCRFs). The subject should continue to complete all safety assessments at subsequent study visits up to and including Day 28.

4.4.2 Criteria for Study Termination

In the event that any of the following is encountered, the DRC will convene to determine status of study enrollment:

- ≥ 2 subjects are discontinued from treatment for study drug-related safety reasons; and/or
- ≥ 2 subjects experience similar SAEs or Grade 3 (CTCAE version 5.0) AEs regardless of relatedness to study drug.

The following will not be considered as criteria for study termination:

- Grade 3 to 4 fever if present at study entry;
- Grade 3 nausea if resolves to \leq Grade 1 within 72 hours; and/or
- Grade 3 fatigue, malaise, or insomnia if resolves to \leq Grade 1 within 72 hours.

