8.1.3 Assessment of Adverse Events by the Investigator

The Investigator is responsible for the detection and documentation of events meeting the criteria and definitions of an AE or SAE as described in this protocol. The Investigator will assess the severity (intensity) of each AE according to the CTCAE version 5.0, and will also categorize each AE as to its potential relationship to study drug using the categories of yes or no.

Assessment of Severity

The severity of all AEs should be graded according to the CTCAE version 5.0. For those AE terms not listed in the CTCAE, the following grading system should be used:

- CTCAE Grade 1: Mild; asymptomatic or mild symptoms; clinical or diagnostic observations only; intervention not indicated;
- CTCAE Grade 2: Moderate; minimal local or noninvasive intervention indicated; limiting age-appropriate instrumental activities of daily living;
- CTCAE Grade 3: Severe or medically significant but not immediately life-threatening; hospitalization or prolongation of hospitalization indicated; disabling; limiting self-care activities of daily living;
- CTCAE Grade 4: Life-threatening consequences; urgent intervention indicated; and
- CTCAE Grade 5: Death related to the AE.

It is important to distinguish between severe AEs and SAEs. Severity is a classification of intensity, whereas an SAE is an AE that meets serious criteria, as described in Section [8.2](#).

Causality Assessment

The relationship of an AE to the administration of the study drug is to be assessed according to the following definitions:

No (unrelated, not related, unlikely to be related) – The time course between the administration of study drug and the occurrence or worsening of the AE rules out a causal relationship and another cause (concomitant drugs, therapies, complications, etc) is suspected.

Yes (possibly, probably, or definitely related) – The time course between the administration of study drug and the occurrence or worsening of the AE is consistent with a causal relationship and no other cause (concomitant drugs, therapies, complications, etc) can be identified.

The definition implies a reasonable possibility of a causal relationship between an AE or SAE and the study drug. This means that there are facts (evidence) or arguments to suggest a causal relationship.

The following factors should also be considered:

- The temporal sequence from study drug administration;

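### The one DRC trigger that ignores relatedness says Grade 3, not Grade 3 or higher, so read literally it misses some non-serious Grade 4 clusters

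*Protocol*

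**What the plan says.** Protocol 4.4.2 convenes the DRC on either of two findings, each needing at least two subjects.

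- **First trigger:** "subjects are discontinued from treatment for study drug-related safety reasons".
- **Second trigger:** "subjects experience similar SAEs or Grade 3 (CTCAE version 5.0) AEs regardless of relatedness to study drug". It has an SAE limb and a grade limb.

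A short list of exemptions follows, beginning with "Grade 3 to 4 fever if present at study entry".

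Protocol 4.4.1, on stopping study drug in one subject, writes the threshold with a ≥ sign in three places: for an "AE or clinically significant laboratory abnormality considered related to study drug", for the injection reaction ("\geq Grade 3 (CTCAE version 5.0) injection reaction in the first 24 hours post-injection"), and for a blood pressure drop needing intervention.

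Protocol 8.1.3 grades severity by CTCAE 5.0 and supplies its own scale for terms that CTCAE does not list. It states that severity and seriousness are different things. SAP section 4 describes the DRC but does not restate the 4.4.2 triggers, and no other text in either document corrects or extends them.

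**The concern.** A safety threshold should not become harder to meet as events become more severe. As printed, the grade limb of the second trigger names one grade only. A pair of similar Grade 3 AEs obliges the DRC to meet. The same pair at Grade 4 may not, if the events are not classed as serious and no drug-related discontinuation follows.

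The relatedness-free trigger matters here because the subjects are acutely ill, receive other COVID-19 treatments, and will often have another possible cause for an event. The 8.1.3 definition of a related event requires that no other cause can be identified. A trigger that does not depend on causality protects against clusters being explained away one subject at a time. What is at stake is a possible delay before the DRC looks at such a cluster.

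**Working it through.** No figure in the plan needs reproducing, and no arithmetic bears on the trigger itself. The check applies both 4.4.2 triggers, as written and then with the sign added, to two subjects with similar AEs.

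**Inputs**

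- Triggers: Protocol 4.4.2.
- Mandatory stop for a related AE of Grade 3 or higher: Protocol 4.4.1.
- Seriousness: Protocol 8.2. The criteria include death, life-threatening (limited to immediate risk of death at the time), prolonged hospitalization and important medical event, in the view of the Investigator or the Sponsor.
- Grade descriptions for terms not listed in CTCAE: Protocol 8.1.3, "CTCAE Grade 3: Severe or medically significant but not immediately life-threatening" and "CTCAE Grade 4: Life-threatening consequences; urgent intervention indicated".
- Timing: dosing lasts 7 days or until discharge or death (5.5.3), extendable to 14 days in Part 2. AEs are collected from first dose to Day 28 (8.1). After a full course this leaves 28 − 7 = 21 days, or 28 − 14 = 14 days if extended, in which AEs are recorded but no drug remains to be stopped.

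**Result: does the DRC have to convene?**

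| Two similar AEs | Grade 3, as written | Grade 4, as written | Grade 4, with ≥ |
|---|---|---|---|
| Serious, any causality | Yes, SAE limb | Yes, SAE limb | Yes |
| Non-serious, related, during dosing | Yes, grade limb | Yes, by discontinuation under 4.4.1 and the first trigger | Yes |
| Non-serious, related, after last dose | Yes, grade limb | **No** | Yes |
| Non-serious, unrelated, any time | Yes, grade limb | **No** | Yes |

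Grade 5 is death, which is always an SAE, so it is never missed.

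**Can the two missed rows contain events?** In principle, yes. Section 8.1.3 separates severity from seriousness, 8.2 restricts the life-threatening criterion to immediate risk of death, and 8.1 counts laboratory findings as possible AEs. A high-grade laboratory AE that is not serious is therefore possible. The documents do not show which events would fall there or how often.

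**Was Grade 4 meant to count?** Probably. If Grade 4 AEs were outside the grade limb, that limb would not need a fever exemption reaching to Grade 4. This is suggestive only, because the exemption could also serve to keep a serious fever out of the SAE limb.

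**Could the sign simply have dropped out of the text?** This cannot be fully excluded. But the same bullet keeps its ≥ before the number of subjects, and the exemptions below it keep their ≤ signs.

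**The case against.** The strongest reply is that the gap may be nearly empty and that nobody would apply the rule literally. For terms outside CTCAE, 8.1.3 describes Grade 4 as life-threatening with urgent intervention, and under 8.2 either the Investigator or the Sponsor can make an event serious. A judgment of unrelated requires, under 8.1.3, that the time course rules out causality and another cause is suspected. The DRC also meets on schedule, study personnel and the Medical Monitor carry out ad hoc safety reviews (3.2), and the Charter may settle the point.

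Most of this stands, and it limits the size of the problem. It does not remove it. The 8.1.3 descriptions are introduced by "For those AE terms not listed in the CTCAE, the following grading system should be used", so they do not govern listed terms. The important-medical-event criterion rests on judgment. Ad hoc reviews do not oblige the DRC to meet. The site's notice to the Sponsor or Medical Monitor before stopping drug (4.5) is waived in a life-threatening situation, so it is a weak safeguard for Grade 4 events.

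Three stronger readings are tempting, and the documents do not support them.

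- **That life-threatening clusters in general escape the DRC.** They do not: an event with immediate risk of death is an SAE and enters through the SAE limb.
- **That the second trigger is the protocol's only safety rule free of a relatedness test.** It is the only such event-based trigger for convening the DRC. In 4.4.1, the injection-reaction and anaphylaxis rules, and the rule for a blood pressure drop needing intervention, stop drug in an individual without a stated relatedness condition.
- **That the spacing of DRC meetings measures the gap.** About 30 − 6 = 24 subjects follow the sentinels in each Part 1 step, and about 0.25 × 120 = 30 enroll between Part 2 reviews. Those figures describe the calendar and would be the same for any missed trigger.

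**Conclusion.** Wrong as written, and small. Taken literally, 4.4.2 obliges the DRC to convene for two similar non-serious Grade 3 AEs but not for the same events at Grade 4, when these are unrelated or are related but arise after dosing has ended. The likely explanation is a drafting slip.

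The conclusion rests on the printed wording and on the absence of correcting text in the protocol or SAP. It assumes that the DRC Charter, which is not available here, does not already set the threshold at Grade 3 or higher. The practical consequence is at most a later DRC review of a narrow class of events. With no event rate in the documents, neither a probability nor a number of affected subjects can be given.

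**What to change.** In the second trigger of Protocol 4.4.2, insert ≥ immediately before Grade 3, so that the grade limb covers Grade 3 and above, and leave the rest of the sentence unchanged. Keep the exemption list as it stands. Align the DRC Charter if it repeats the wording.

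The edit is one symbol, but under Protocol 12.1 an amendment goes through the same review and approval as the original protocol and needs IRB approval, with approximately 20 sites planned. It does not justify an amendment of its own. It can be bundled with the next one, with a clarification in the Charter meanwhile. The running cost is at most an occasional extra DRC meeting.

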4.5 Withdrawal and Discontinuation Criteria

Subjects may be withdrawn from the study for the following reasons:

- Withdrawn consent by subject or LAR; or
- Loss to follow-up.

In addition to the criteria listed in Section 4.4.1, subjects may be discontinued from study drug (but will continue to be followed in the study) for any of the following reasons:

- Occurrence of any medical condition or circumstance that exposes the subject to substantial risk and/or does not allow the subject to adhere to the requirements of the protocol;
- Any SAE, clinically significant AE, severe laboratory abnormality (eg, worsening renal or hepatic impairment), intercurrent illness, or other medical condition which indicates to the Investigator that continued participation is not in the best interest of the subject;
- Pregnancy;
- Requirement of prohibited concomitant medication;
- Subject failure to comply with protocol requirements or study-related procedures; or
- Termination of the study by the Sponsor or the regulatory authority.

Prior to subject discontinuation from study drug, the site should notify the Sponsor or Medical Monitor, unless the subject is in a life-threatening situation.

If a subject discontinues from study drug prematurely due to the above criteria or any other reason, site staff should make every effort to complete the full panel of assessments scheduled for the Day 7 visit (except study drug administration). Subjects who discontinue study drug should continue to complete all safety assessments at subsequent study visits up to and including Day 28, unless the subject or LAR withdraws consent or is lost to follow-up. The reason for subject discontinuation from study drug or study withdrawal must be documented in the source and eCRFs.

If, after a subject is discharged, the subject is lost to follow-up, attempts to contact the subject must be made and documented in the source.

Randomized subjects who have received a dose of study drug will not be replaced.

5 STUDY TREATMENTS

5.1 Treatment Groups

Subjects will be randomized to 1 of the following treatment groups in Part 1, Step 1:

- Razuprotafib 10 mg TID;
- Razuprotafib 20 mg TID; or
- Placebo TID.

Subjects will be randomized to 1 of the following treatment groups in Part 1, Step 2:

- Razuprotafib 20 mg TID;
- Razuprotafib 30 mg TID; or
- Placebo TID (the placebo volume will match the active volume for each treatment group).

Note: The planned dosing for Part 1, Step 2 may be changed after the DRC reviews the safety and PK data from Part 1, Step 1.

Subjects will be randomized to 1 of the following treatment groups in Part 2:

- Dose 1 razuprotafib TID (dose may be recommended by the DRC up to 20 mg TID);
- Dose 2 razuprotafib TID (optional; dose may be recommended by the DRC up to 30 mg TID); or
- Placebo TID (the placebo volume will match the active volume for each treatment group).

The dosage(s) for Part 1, Step 2 and Part 2 are contingent upon DRC recommendation. If 2 razuprotafib dose levels are chosen, subjects will be randomized 1:1:1 to dose 1, dose 2, or placebo. If 1 razuprotafib dose level is chosen, subjects will be randomized 2:1 (razuprotafib:placebo).

5.2 Rationale for Dosing

Previous clinical studies with razuprotafib have evaluated 15 mg and 30 mg BID dosing regimens, administered by SC injection, in diabetic patients with eye diseases. In all of the studies conducted, razuprotafib has exhibited a predictable, dose-dependent PK profile. Also, the results have clearly confirmed target engagement of razuprotafib as evidenced by a dose-dependent decrease in blood pressure, the effect that has been associated with a downstream effect of razuprotafib on Tie2 activation resulting in an increase in eNOS. The effect on blood pressure has been transient in duration and is a function of the C_{max} value for the razuprotafib dose. In human studies, the PK profile exhibited a rapid increase in plasma concentration after SC dose administration with time to C_{max} values achieved within 15 to 30 minutes, followed by a rapid decline with a $T_{1/2}$ of approximately 1 hour. Due to the short $T_{1/2}$, no significant razuprotafib accumulation is expected when administered on a TID regimen in this study.

Based on the unknown pharmacologic effects of razuprotafib in patients with COVID-19, this study is designed as a 2-part, placebo-controlled, parallel-group study with appropriate safety monitoring and PK assessments (see [Figure 1](#)). Part 1 will be a 2-step dose escalation conducted in approximately 60 subjects assessing doses of up to 30 mg TID, and Part 2 will be a

proof-of-concept safety and efficacy study conducted in approximately 120 subjects. In this study, administering study drug on a TID frequency in the hospital setting is feasible and provides additional safety mitigation by dividing a total daily dose into smaller individual doses. In particular, the TID regimen would mitigate the C_{max} -related blood pressure effects. In addition, the initial doses of 10 mg and 20 mg TID proposed in Part 1, Step 1 do not exceed the highest daily dose that was evaluated in previous clinical studies in diabetic patients. In addition to standard of care blood pressure monitoring, following each dose of the TID regimen, timed blood pressure assessments will be conducted to monitor safety. The proposed design ensures that a full safety and PK review of the 10 mg and 20 mg TID doses (Part 1, Step 1) is conducted by the DRC prior to dose escalating to up to 30 mg TID (Part 1, Step 2). In addition, following dose escalation, a second safety evaluation will be conducted to assess the safety and PK of the doses evaluated in Part 1, Step 2 and to select doses for the larger proof-of-concept evaluation in approximately 120 subjects (Part 2). The doses selected for this study are supported by the preclinical toxicology data generated for razuprotafib. The study design includes PK sampling, appropriate safety monitoring, periodic formal review of the safety data for dose escalation and continued safety of the subjects, individual stopping rules, and interim safety analyses. Moreover, multiple biomarkers are planned to be analyzed to evaluate the effect of razuprotafib dosing and changes in COVID-19-related effects.

